## Hospitalization

SREs are associated with significant health resource utilization. In a recent multicenter, observational study designed to describe cross-regional differences in health resource utilization of SREs in Europe and US, Durah et al. 18 reported 25% of reported SREs required inpatient hospitalization with mean of 18 days stay. Furthermore, 96% of the SREs resulted in inpatient and/or outpatient procedures, with radiation therapy to bone being the highest SRE type associated with highest number of procedures. In another study, 26% of SREs were associated with inpatient hospital stay with mean duration of 19.5 days 19. Interventions that prevent the development of SREs have been shown to significantly reduce costs associated with SREs 20, accounting for the costs of interventions. SREs result in considerable health resource utilization and impose a substantial financial burden. This study will be investigating the impact of upfront radiation therapy on the number of hospitalizations related to SREs in patients with high risk bone metastases.

Page **9** of **30** Version: 2/26/16

#### Innovation

The current standard of care of radiation for symptomatic bone lesions, which was established in the 1980s when the prognosis of patients with metastatic cancer was inferior to what it is now, and thus, may no longer be appropriate for metastatic cancer patients in the modern era of improved systemic therapy. There are several theoretical benefits to early, upfront RT of asymptomatic or minimally symptomatic bone metastases, such as reducing the risk for SREs. Furthermore, risks for developing painful bone metastases can be also reduced with early RT therefore improving pain-free survival and quality of life. Finally, there are significant direct and indirect costs associated with hospitalizations for painful bone metastases. This trial proposes the evaluation of a new treatment paradigm, in which bone metastases are treated with upfront RT before they become symptomatic in the outpatient setting.

#### 4.0 OVERVIEW OF STUDY DESIGN/INTERVENTION

# 4.1 Design

This is a randomized (1:1) single institution trial in patients with metastatic solid tumors. Subjects will be randomized to receive either standard of care or upfront, early RT to high risk bone followed by standard of care therapy at the discretion of the treating medical oncologist. At the time of randomization, physicians will fill out the Lesions Identification Worksheet (Appendix) to document the ≤5 highest risk bone metastases per protocol definition to be followed during the protocol in both arms.

## 4.2 Intervention

#### 4.2.1 Standard of Care

Patients randomized to Arm 1 will undergo appropriate therapy as determined by their oncologist. These patients will either continue their current therapy or be transitioned to a new standard of care therapy at the discretion of the treating oncologist. If randomized to Arm 1, these patients may undergo palliative RT for progressive, painful lesions (a skeletal related event) at time of symptom development (not upfront palliative RT).

## 4.2.2 Upfront, Early RT

Patients enrolled on Arm 2 of the study will undergo selective RT to 5 or less high risk bone metastases defined as 1. bulkiest sites of osseous disease ≥ 2cm, 2. disease involving the hip (acetabulum, femoral head, femoral neck), shoulder (acromion, glenoid, humeral head), or sacroiliac joints 3. disease in long bones with1/3-2/3 cortical thickness (humerus, radius, ulna, clavicle, femur, tibia, fibula, metacarpus, phalanges) 4. disease in junctional spine (C7-T1, T12-L1, L5-S1) and/or disease with posterior element involvement. Bone metastases that are within 3cm of each other will be treated as one site. Patients may undergo systemic therapy concurrently with RT at the discretion of

Page **10** of **30** Version: 2/26/16

treating radiation oncologist and medical oncologist. After completion of RT, patients will continue standard of care therapy per the treating oncologist.

# 4.2.3 Brief Pain Inventory Short Form

Patients enrolled on either arm will undergo assessment of patient reported cancerspecific pain questionnaire using the Brief Pain Inventory Short Form at baseline, 3 months, 6 months, 12 months and optionally but recommended within one week of any SRE (Appendix, ~5 minutes to complete). For patients randomized to receive upfront, early RT, they will complete the form once every 5 treatment days during RT. The Brief Pain Inventory is a validated method in rapidly assessing the severity of pain and its impact on functioning. It is a 9 item self-administered questionnaire used to evaluate the severity of a patient's pain and the impact of this pain on the patient's daily functioning. Patients are asked to rate their worst, least, average, and current pain intensity, list current treatments and their perceived effectiveness, and rate the degree that pain interferes with general activity, mood, walking ability, normal work, relations with other persons, sleep, and enjoyment of life on a 10 point scale. Patients will be able to rate their pain on a 0 to 10 scale, 0 being no pain and 10 being the worst pain, for different time points (within the last 24 hours, on average, at the time of filling out the form). Patients will also be asked what treatments or medications they are receiving for pain from their understanding, and how much relief they received from the pain treatment and medications (0% being no relief and 100% being complete relief). Patients will also evaluate how much the pain has interfered with their activities and function (0 being does not interfere and 10 being completely interferes).

## **4.2.4 EuroQol**, **EQ-5D-5L**

Patients enrolled on either arm will undergo assessment of patient reported health utilities using the EuroQol EQ-5D-5L questionnaire at baseline, 3 months, 6 months, 12 months, and optionally but recommended within one week of any SRE (Appendix, ~10 minutes to complete). For patients randomized to receive upfront, early RT, they will complete the form prior to RT. It is a standardized instrument created by the EuroQol Group as a measure of health utility. It is a generic global quality of life measurement tool. It consists of a descriptive system that includes 5 dimensions (5D, each measured by a single item) (mobility, self-care, usual activities, pain/discomfort, and anxiety/depression) each of which can be assessed on 5 levels (5L) (no problems, slight problems, moderate problems, severe problems, and extreme problems). Respondents are asked to indicate which response option best describes their health "today".

Respondents are asked to indicate their health state by marking the box associated with the most appropriate statement in each of the 5 dimensions, resulting in a one digit number expressing the level selected for that dimension (1-5 from no problems to extreme problems, note these do not carry numeric value and should not be summarized as such)

- The digits for the 5 dimensions are then combined into a 5-digit code describing the respondent overall health state

Page **11** of **30** Version: 2/26/16

- The 5-digit health states are then transformed to overall index values (sometimes called preference values, utilities, or QALY weights) based on country-specific value sets provided by the EuroQol Group. The United States value set will be used to obtain the overall index values and are available at http://www.euroqol.org/about-eq-5d/valuation-of-eq-5d/eq-5d-5l-value-sets.html for the current study. The index value has interpretive anchors at 0 (dead) and 1 (best possible health).

- In order to minimize missing values on the overall index value, missing values are given a numeric value of 9; ambiguous values (i.e. two responses to the same question) are also given a numeric value of 9 and are accounted for in the published overall index values.

# 5.0 THERAPEUTIC/DIAGNOSTIC AGENTS

# 5.1 Radiation Therapy

Radiation therapy will be delivered according to department standards. For this protocol, total dose and dose fractionation may be delivered at the discretion of the treating radiation oncologist according to department standards. All techniques including conventional, 3D-CRT, or IMRT technique may be used. Image guidance at the time of treatment delivery to verify patient positioning may be chosen at the discretion of the treating radiation oncologist according to department standards.

## 5.2 Systemic Therapy

Standard of care systemic therapy, including chemotherapeutics, targeted therapies, immunomodulatory agents, and hormonal therapies will be delivered at the discretion of the treating medical oncologist. Patients may receive systemic therapy concurrently and there are no restrictions on initiation of systemic agents after radiotherapy including immunotherapy and hormonal therapy, the timing of which will be determined by a consensus between the treating medical and radiation oncologists.

# 6.0 CRITERIA FOR SUBJECT ELIGIBILITY

Describe the characteristics of the patient/subject population.

# 6.1 Subject Inclusion Criteria

- Histologically confirmed solid tumor malignancy with greater than 5 sites of metastatic disease detected on imaging.
- Has high risk bone metastases that are asymptomatic or minimally symptomatic (not requiring opioids). High risks metastases are defined as: 1. bulkiest sites of osseous disease ≥ 2cm, 2. disease involving the hip (acetabulum, femoral head, femoral neck),

Page **12** of **30** Version: 2/26/16

shoulder (acromion, glenoid, humeral head), or sacroiliac joints 3. disease in long bones with1/3-2/3 cortical thickness (humerus, radius, ulna, clavicle, femur, tibia, fibula, metacarpus, phalanges) 4. disease in junctional spine (C7-T1, T12-L1, L5-S1) and/or disease with posterior element involvement.

- ECOG performance status 0 − 2.
- Age ≥ 18 years.
- Able to provide informed consent.
- Patients at reproductive potential must agree to practice an effective contraceptive method. Women of childbearing potential must not be pregnant or lactating.

# 6.2 Subject Exclusion Criteria

- Previous radiotherapy to the intended treatment site that precludes developing a treatment plan that respects normal tissue tolerances.
- Serious medical co-morbidities precluding radiotherapy.
- Pregnant or lactating women.
- Target lesion(s) is/are complicated bone metastases that include clinical or radiological evidence of spinal cord compression or impending pathological fracture.
- Leptomeningeal disease.
- Malignant pleural effusion.
- Absolute neutrophil count (ANC) <1.0 K/mcL and platelet count <50 K/mcL at time of enrollment.
- Patients whose entry to the trial will cause unacceptable clinical delays in their planned management.

## 7.0 RECRUITMENT PLAN

A member of the patients treatment team, the site protocol investigator, or research team at Memorial Sloan-Kettering Cancer Center (MSKCC) will identify potential research participants. If the investigator is a member of the treatment team, s/he will screen their patient"s medical records for suitable research study participants. Potential subjects contacted by their treating physician will be referred to the investigator/research staff of the study.

The site principal investigator may also screen the medical records of patients with whom they do not have a treatment relationship for the limited purpose of identifying patients who would be eligible to enroll in the study and to record appropriate contact information in order to approach these patients regarding the possibility of enrolling in the study.

During the initial conversation between the investigator/research staff and the patient, the patient may be asked to provide certain health information that is necessary to the recruitment and enrollment process. The investigator/research staff may also review portions of their medical records at MSKCC in order to further assess eligibility. They will use the information provided by the patient and/or medical record to confirm that the patient is eligible and to contact the patient regarding study enrollment.

In most cases, the initial contact with the prospective subject will be conducted either by the treatment team, investigator or the research staff working in consultation with the

Page **13** of **30** Version: 2/26/16

treatment team. The recruitment process outlined presents no more than minimal risk to the privacy of the patients who are screened and minimal PHI will be maintained as part of a screening log. For these reasons, we seek a (partial) limited waiver of authorization for the purposes of (1) reviewing medical records to identify potential research subjects and obtain information relevant to the enrollment process; (2) conversing with patients regarding possible enrollment; (3) handling of PHI contained within those records and provided by the potential subjects; and (4) maintaining information in a screening log of

# 8.0 PRETREATMENT EVALUATION

The following tests must be completed prior to enrollment unless otherwise specified:

Prior to study entry (randomization):

patients approached (if applicable).

• Standard of care biopsy proving malignancy, with clinical documentation consistent with metastatic disease, per physician discretion.

Within 6 weeks (42 days) of study entry (randomization):

- CT CAP, FDG-PET/CT scan, MRI Total Spine or NaF-PET can be used, imaging study is at the discretion of the treating physician.
- Other local imaging studies that include the target lesion(s) can also be used as baseline imaging at the discretion of the treating physician.

Within 4 weeks (28 days) of study entry (randomization):

- CBC with differential
- Comprehensive metabolic panel (CMP=Na, K, Cl, CO2, BUN, Creatine, Ca, Glucose, total protein, albumin, alk phos, total bilirubin, AST and ALT).
- Complete medical history including current medications, comorbidities and performance status
- Physical exam including weight, height and vital signs (O2 saturation, blood pressure, heart rate, respiratory rate, and temperature).
- BPI short form and EQ-5D-5L
- Lesion Identification Worksheet should be completed by physicians

#### 9.0 TREATMENT/INTERVENTION PLAN

Patients who have metastatic cancer and greater than 5 sites of disease will be enrolled. Patients may also have newly diagnosed stage IV disease. Patient will be randomized to standard of care therapy or to receive RT to selective bone metastases prior to continuation of standard therapy.

9.1 RT

Page **14** of **30** Version: 2/26/16

Patients will undergo RT to each lesion using one of the dose and fractionation regimens in the table below. Accounting for the patient"s global clinical status, the treating radiation oncologist should select a RT regimen that would result in optimal lesion local control while not exceeding local normal tissue radiation tolerance:

Page **15** of **30** Version: 2/26/16

Total Dose	Fractions	Dose per Fraction	Verification Imaging
2000cGy	5	400cGy	MV or KV
3000cGy	10	300cGy	MV or KV
3000cGy	5	600cGy	KV and CBCT
3500cGy	5	700cGy	KV and CBCT
2400cGY	3	800cGy	KV and CBCT
2700cGy	3	900cGy	KV and CBCT
2400cGy	1	2400cGy	KV and CBCT

Patients will first be simulated using appropriate immobilization as determined by the treating radiation oncologist. This will be followed by acquisition of a CT scan in the treatment position. The use of intravenous or oral contrast will be at the discretion of the treating radiation oncologist. Dose constraints will be followed according to department standards and will depend on the radiation technique and total dose prescribed.

The treating radiation oncologist must delineate the gross tumor volume (GTV). Clinical target volume (CTV) will be defined as the GTV plus a margin required for microscopic extension of tumor. The planning target volume (PTV) should expand the CTV by an amount necessary to account for uncertainty in patient positioning and treatment delivery.

## 10.0 EVALUATION DURING TREATMENT/INTERVENTION

All patients in Arm 2 (RT arm) will be assessed for toxicities according to CTCAE v 4.0 and pain score using BPI short form once every 5 treatment days. Only patients in Arm 2 (RT arm) will have radiation treatment related adverse event evaluation. Following randomization, all patients in Arm 1 and Arm 2 will be scheduled for follow-up at 3 months (+/- 4 weeks), 6 months (+/- 4 weeks), 12 months (+/- 4 weeks), and receive the following assessments:

- CBC with differential
- Imaging studies (Follow-up imaging at the discretion of the treating physicians)
- History and physical
- Performance status
- Adverse event evaluation (CTCAE V 4.0) (Excluding Arm 1 patients)
- BPI Short Form
- EQ-5D-5L

•

In the event of an SRE, the following assessments should be completed within one week. As it may not be feasible that the research team will be notified of all SREs within one week, or a patient may not be able to come to MSK, these assessments are optional, but highly recommended:

- CBC with differential
- Imaging studies (Follow-up imaging at the discretion of the treating physician)
- History and physical
- Performance status
- Adverse event evaluation (CTCAE v 4.0)
- BPI Short Form
- EQ-5D-5L

If patient is unable to come in for a follow-up appointment or within one week of an SRE occurring, a telephone follow-up will suffice. The CBC with differential, history and physical, performance status and imaging studies will be deferred. If the patient has had any of these assessments completed locally, records should be obtained to fulfill these requirements. If the attending physician is able, the adverse event evaluation can be completed over the phone.

Additionally, the BPI Short Form and EQ-5D-5L can be completed over the phone or sent to the patient via mail, fax or electronic mail by the physician, physician office assistant or research staff. For SRE, it is preferred that the BPI Short Form and EQ-5D-5L are completed over the phone if patients are unable to come in for a follow-up appointment. If the patient cannot be reached by phone or prefers to complete the questionnaires personally, the questionnaires will be sent via mail, fax or electronic mail. The questionnaires sent directly to patients must be blank forms with no patient identifiers, only study ID numbers. If questionnaires are sent via mail, the patient must be provided with a pre-filled business envelope that will allow patients to return it with no expense. Patients must also have the option of returning questionnaires by electronic mail or fax. If a patient is unable to come in for a follow-up appointment or complete the questionnaires over the phone, the method by which questionnaires are sent to patients and the method by which questionnaires are returned will be determined based on the patient's preference or if they are unable to be contacted by phone, the contact information on file for the patient as some patients may not have access to a phone, fax or electronic mail.

Page **17** of **30** Version: 2/26/16

	Prior to randomizati on	Within 4 weeks prior to randomiz ation	Once every 5 treatment days during radiation	3 months following randomizat ion +/- 4 weeks	6 months following randomizat ion +/- 4 weeks	12 months following randomizat ion +/- 4 weeks	Within one week of SRE 
Standard of care biopsy of a metastatic lesion or pathology review confirming metastatic cancer 	Х						
CBC with differential		X		X	X	X	X
CMP		Х					
lmaging studies 		Х		X 	X 	X 	X 
History and physical		X		X 	X 	X 	X 
Performance status		Х		X	X	Х	Х
Adverse event evaluation (CTCAE v 4.0)			X	X	X	X	Х
BPI Short Form		Х	Х	Х	Х	Х	X
EQ-5D-5L		Х		X	X	X	X
Lesions Identification Worksheet		Х					

<sup>1 For patients with prostate cancer, an elevated PSA consistent with metastatic disease is adequate in the absence of a biopsy.

<sup>2 Follow up imaging at the discretion of the treating physician. The same imaging modality is encouraged for assessment between time points.

<sup>3 Patient's height is not needed at follow ups and SRE.

<sup>4 All assessments following an SRE are optional, but highly recommended

<sup>5 Baseline imaging can be obtained within 6 weeks of study entry

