Palliative radiation therapy is a well-established, frequently used treatment for patients with metastatic disease. It is often the standard of care for patients with symptomatic metastatic lesion. It is extremely unlikely to be more toxic or cause earlier deaths.

We expect to enroll all 74 patients within 2 years.

Secondary objectives will be analyzed per patient. Unless otherwise specified, all endpoints are defined within the time window from the date of randomization to death or 12 months, whichever occurs first.

To compare the number of hospitalizations related to SREs between standard of care and upfront, early palliative RT arms we will employ a Wilcoxon rank sum test.

To compare quality of life between standard of care and RT arms, using the Brief Pain Inventory (BPI) and EuroQol Group EQ-5D-5L forms, we will test the difference (between the two arms) of the survey results at the following time points: 3 months, 6 months, 12 months and optionally but recommended within one week of any SRE. The individual quantitative scores derived from the BPI, and the utility scores as well as the overall health scores derived from EQ-5D-5L, will be summarized at these assessment times using descriptive statistics (means and standard deviations, medians and quartiles). Differences between the two arms in terms of these quantitative scores at various time points of interest will be evaluated for both statistical and clinical significance using Wilcoxon rank

Page **22** of **30** Version: 2/26/16

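### Arm 1 is excluded from the scheduled CTCAE evaluation, so early RT has no scheduled toxicity comparator, and the adverse event rules conflict across sections

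*Combined protocol and SAP*

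**What the plan says.** **Visits.** Section 10.0 states that "all patients in Arm 1 and Arm 2 will be scheduled for follow-up at 3 months", then at 6 and 12 months. Both arms have a CBC, history and physical, performance status, BPI and EQ-5D-5L.

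**Adverse events at those visits.** The list item is "Adverse event evaluation (CTCAE V 4.0) (Excluding Arm 1 patients". The same section says "Only patients in Arm 2 (RT arm) will have radiation treatment related adverse event evaluation".

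**RT in Arm 1.** Under Section 4.2.1, "these patients may undergo palliative RT for progressive, painful lesions (a skeletal related event) at time of symptom development".

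**Around an SRE.** Section 10.0 says "In the event of an SRE, the following assessments should be completed within one week". That list includes a CTCAE evaluation with no Arm 1 exclusion, but "these assessments are optional, but highly recommended".

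**Objective and analysis.** Sections 2.0 and 14.0 confine the toxicity objective and its descriptive tabulation to the upfront RT arm. On the possibility of harm from RT, Section 14.0 says "It is extremely unlikely to be more toxic or cause earlier deaths".

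**The concern.** The trial asks whether to irradiate now or wait, in patients with few or no symptoms. In that setting the added toxicity of acting early is part of the answer. Several RT toxicities listed in Section 11.0 (fatigue, nausea and vomiting, low blood counts leading to infection) can also arise from advanced disease or systemic therapy, and Sections 4.2.2 and 5.2 allow systemic therapy alongside RT. A table from Arm 2 alone mixes RT effects with this background. The randomized control arm is the direct way to estimate the background, and its patients are already being examined at the same visits.

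There is also an operational problem. Sections 10.0, 11.1, 13.0 and 17.2 give site staff different answers on whose adverse events are recorded and for how long.

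**Working it through.** **1. Which passages would put an Arm 1 adverse event on record?**

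| Place | Rule | Arm 1 covered? |
|---|---|---|
| Section 10.0, visit list | CTCAE at 3, 6, 12 months | No, expressly excluded |
| Section 10.0, schedule table | CTCAE marked at 3, 6, 12 months and at an SRE | Yes on its face; no arm footnote |
| Section 10.0, SRE list | CTCAE within one week of an SRE | Not excluded, but optional |
| Section 11.1 | New adverse events recorded; all events after the first RT dose reported | No arm named; could cover delayed RT |
| Section 11.2.1 | Grade ≥3 non-hematologic events recorded | No arm named |
| Section 17.2 | SAE reporting runs from the start of the investigational treatment | In effect no, since Arm 1 never starts it |
| Section 13.0 | On protocol for 12 months or until an SRE | Visits may stop when delayed RT is given |
| Sections 2.0 and 14.0 | Toxicity evaluated and tabulated | Upfront RT arm only |

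The visit list cannot be followed together with the schedule table. Section 11.1 can be read as reaching Arm 1 after delayed RT, but the visit list removes the scheduled evaluation at which such events would be found. The optional evaluation within a week of an SRE comes too early for later effects of RT given for that SRE.

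**2. Patients per arm.** Section 14.0 gives event rates of 60% and 30%, one-sided alpha 0.05 and power above 80%. With pooled variance and no continuity correction:

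n = [1.645·√(2·0.45·0.55) + 0.842·√(0.24 + 0.21)]² / 0.30² ≈ 33 per arm, or 66 in total.

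The 10% allowance gives 66/0.90 = 73.3, rounded up to 74. Both figures match the plan. Allocation 1:1 gives about 37 per arm.

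**3. Arm 1 patients who might receive delayed RT.** No number is stated. Applying the planned 60% to patients gives 0.60 × 37 ≈ 22. This is only a rough ceiling, because Section 14.0 defines the rate per lesion and it covers all SRE types. At an assumed 20% the figure is 0.20 × 37 ≈ 7.

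**4. What Arm 2 alone can show.** With zero events of a given type in 37 patients, the one-sided 95% upper limit is 1 − 0.05^(1/37) = 7.8%, with no control rate beside it.

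**5. What collection in both arms would add.** With equal true rates p and 37 per arm, the 95% half-width for the difference is 1.96·√(2p(1−p)/37). The last column is the Arm 2 rate needed for 80% power with a two-sided 0.05 pooled test. The documents give no adverse event rates, so every p is an assumption.

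| Assumed rate | 95% half-width | Arm 2 rate for 80% power |
|---|---|---|
| 5% | about 10 points | about 29% |
| 10% | about 14 points | about 37% |
| 20% | about 18 points | about 51% |

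**6. Burden.** 37 patients × 3 visits = at most 111 forms, fewer after deaths and withdrawals.

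**The case against.** The exclusion is deliberate and fits the stated objective, which is to describe toxicity in the upfront RT arm. No between-arm toxicity comparison is promised. Section 14.0 gives a reason: palliative RT is established and often standard for symptomatic lesions. Sections 11.1 and 11.2.4 require each event to be attributed, which handles part of the background. The sample is also too small to detect any but large differences. All of this stands. It explains the choice and limits what a change would yield, but attribution by judgment is weaker than a randomized comparator.

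A reader might go further and infer three things that the documents do not support:

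- **That harm is not compared at all.** Overall survival, SRE hospitalizations, BPI and EQ-5D-5L are compared in both arms, and pathological fractures count in the primary endpoint in both. What is missing is the scheduled CTCAE comparison.
- **That Arm 1 adverse events can never be recorded.** The schedule table, the optional SRE list and Section 11.1 do not bar them. The finding there is a contradiction, not a uniform ban.
- **That most Arm 1 patients will receive RT.** Section 4.2.1 only says that they may.

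**Conclusion.** The point holds in this form: the trial has no scheduled CTCAE comparator for early RT, and the rules for recording adverse events contradict one another. The statement in Section 14.0 about greater toxicity therefore cannot be checked against scheduled CTCAE data, although its part about earlier deaths can be examined through overall survival.

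The gap concerns safety description. It does not touch the primary test or its sample size, which reproduces. The change is worth making, but the plan does not fail without it. How many Arm 1 patients the gap affects after delayed RT is unknown: about 7 to 22 of 37 if 20% to 60% receive it, with the upper end a rough ceiling. Collecting the data would give a difference with a wide interval (about ±14 points at an assumed 10% rate) and should not be presented as a powered test.

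**What to change.** 1. **Section 10.0:** delete the parenthetical Arm 1 exclusion, amend the sentence restricting RT-related evaluation to Arm 2, and complete the same CTCAE form in both arms at 3, 6 and 12 months, at minimum for Grade ≥3 events.
2. **Sections 10.0 (text and schedule table), 11.1 and 17.2:** reconcile them so that each states which arm it covers and when recording starts and stops.
3. **Section 13.0:** state that adverse event follow-up at the scheduled visits continues after an SRE, up to 12 months from randomization. Without this, item 1 would miss most toxicity of delayed RT. Section 14.0 already counts lesions separately and defines endpoints to death or 12 months, so it too presumes follow-up past a first SRE.
4. **Section 14.0:** tabulate toxicity by arm with confidence intervals for the differences, labelled as estimation. Show Arm 2 events from the on-treatment assessments separately, since Arm 1 has no matching assessment.

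**Cost.** At most 111 additional forms, many of which will record systemic-therapy events, and continued visits for patients who have had an SRE. Patients still on schedule need no new visit.
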